### II. Discuss instructions and precautions

[figure not shown]
Symptomatic hypotension, genital yeast infections (SGLT2i)

### III. Recommended follow-up

*Labs, diagnostic imaging or studies, new consults, follow-up appointments*

### Strategies for intolerance/symptomatic hypotension

- Reduce non-GDMT antihypertensives, half diuretic dose with initiation of RAAS inhibitor or SGLT2i.
- Consider insulin reduction for history hypoglycemic events with SGLT2i.
- Space out administration times for medications
- Move RAAS inhibitors to evening to peak during sleep
- Lower morning doses relative to evening doses

## S2: Interview Guide

### Introduction

Hello, I am Dr. \_\_\_\_\_ calling from the West LA VA Cardiology. We are piloting an effort to proactively reach out to Veterans with heart disease to see how they are doing and improve their medical therapies for heart failure. Is now a convenient time to discuss your heart medications?

- **Yes:** Thank you. Do you have access to a smartphone or computer? May we convert this visit to video?

- **No:** May we request a follow-up phone, video, or in-person visit with our heart failure clinic?

**Yes:** Thank you. [RTC WLA-Cardiomyopathy Clinic]

**No:** Thank you for your time. [Chart review note for PMD and last cardiology fellow/attending highlighting potential opportunity for further medication optimization]

### Obtain history and assess functional NYHA class

1. How have you been feeling? Any change in [dyspnea/orthopnea/edema]?
2. What type of physical activities do you do regularly [walking, exercise, stairs]?
3. Do you know what medications you take for heart failure and how do manage your medications?
4. Have you had issues with any of heart failure medications in the past?
5. Do you check your home blood pressure and weights regularly? What are they?
6. Do you have issues with lightheadedness/dizziness or passing out?

### Make recommendation

*Optimization:* I see that you might benefit from an increase in you \_\_\_\_\_ / I see that you might benefit from an additional medication \_\_\_\_\_/I see you may benefit from stopping one of your non-heart failure blood pressure medications. May we start that today and you can receive the medication in the mail or pick-up from your local VA clinic?

*Hypervolemia:* Increase diuretic regimen and refer for face to face visit within 1 week.

### Discuss appropriate precautions with optimization

Dizziness, orthostasis, follow-up blood tests.

SGLT2i [genital yeast infections/hypoglycemia for IDDM]

### Next steps

- Order medications
- Follow-up appointment
- Required labs
- BMP in one week (MRA), 1-2 weeks (ACE/ARB/ARNI)

### Questions

Do you have any concerns related to medication change? Other questions?

### Feedback

Thank you for your time. This was a call part of our pilot telephone heart clinic program. How would you rate your experience with the heart failure outreach today on a scale 1 to 10 (10 being very appreciated)? Any suggestions to improve the program?

### S3: Clinician Documentation Form

Documentation survey which will guide clinician's chart review and patient conversation. The form will be password-protected and utilize checkbox and short answers for clinician ease.

Clinic Date	Clinician	Start Time	Homeless	Active Substance Use	Female	Last EF	Last cards appt	Last PCP appt
1/1/21	[name]	13:55	x	x	x	35-40%	1/1/21	1/1/21

Phone Call Time	NYHA Class	No Response
9 minutes	III	x

Reasons for no GDMT titration				
Prior intolerance	Prior adverse event	Patient declined	Patient concerned of side effects	Other
x	x	x	x	Cost

Actions Performed						
Number of Rx adjusted	Med adjustment	Labs ordered	Imaging / diagnostic tests	RTC	Patient Letter	Consults
3	Amlodipine stopped	x	x	x	x	x

Feedback	End Time	Comments
9	1415	Straight to voicemail

Clinician Documentation form definitions	
Clinic date	Date today, (mm/dd/yy)
Clinician	Name of clinician (Last, First)
Start Time	Military time at onset of pre-chart
Homeless	Is the veteran currently experiencing homelessness?
Active substance use	Is the veteran actively using substances?
Female	Sex as categorized in EHR
Last EF	Most recent left ventricular ejection fraction on transthoracic echocardiogram, %
Last cards appt	Date of last cardiology clinic visit, (mm/dd/yy)
Last PCP appt	Date of last PCP visit, (mm/dd/yy)
Phone Call Time	Duration of successful phone or video visit
NYHA Class	Based on patient's symptoms and chart review, (1-3)
No response	Indication if no response after 2 attempts
Patient requests later appointment	Indication if patient is interested in further discussion, but busy at this time. Check and order RTC cardiology
Reasons for no GDMT	
Prior intolerance	History of symptomatic bradycardia or hypotension on GDMT
Prior adverse event	History of hospitalization or angioedema related to GDMT titration. History of yeast infection while taking an SGLT2i inhibitor
Patient declined	Patient declined additional or higher doses of medications in the past
Patient concerned of side effects	Patient is concerned of side effects of GDMT
Other	Other reasons cited by patients or on chart review in the comments
Actions Performed	
# medication adjustments	Number of medications adjusted after this visit
Medication adjustment detail	Description of medication adjustment
Labs ordered	If laboratory tests ordered as part of today's plan
Imaging / diagnostic tests ordered	If imaging or diagnostic tests ordered as part of today's plan
RTC	If "return to clinic" order placed to patient's cardiology clinic
Patient Letter	Letter mailed to patient regarding following up with primary care or cardiology regarding heart failure.
New consults	If new consults placed as part of today's plan
Patient feedback	Self-reported experience of conversation and heart failure plan, on a scale of 1 to 10, where 1 means an awful experience and 10 means an exceptional experience
Time (end call)	Military time on completion of phone call
Comments	Noteworthy general observations not contained in fields regarding chart review or patient experience

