### 4.2.2 Secondary outcome

The secondary outcomes of the study will include the following at final evaluation:

1. Active prescriptions for individual classes of GDMT
  - a. ACE/ARB/ARNI
  - b. Beta-Blocker
  - c. MRA
  - d. ARNI
  - e. SGTL2i
2. Hospitalizations
  - a. Total number of any cause hospitalization
  - b. Total number of primary HF hospitalizations
  - c. Proportion of patients with any hospitalization
  - d. Proportion of patients with any HF hospitalization
3. Number of deaths
4. Clinician time spent per patient from opening chart to end of patient-specific intervention and documentation.
5. Health service efficiency
  - a. Number of patients reviewed or contacted per half-day clinic
  - b. Number of medication adjustments (stop, start, titration) per half-day clinic
  - c. Number of laboratory tests ordered per half-day clinic
  - d. Number of imaging/diagnostic procedures ordered per half-day clinic
  - e. Number of referrals for consults/device therapy per half-day clinic
6. Qualitative evaluation of patient surveys who received the intervention.

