## 5 Study Methods

### 5.1 General Study Design and Plan

This is a randomized, pragmatic QI study designed to evaluate the effectiveness of proactive panel management to close gaps in evidence-based care for patients with HFrEF. We will use the VA's ADHFD to generate a list of actionable patients with HFrEF and left ventricular ejection fraction (LVEF)  $\leq 35\%$ . After identifying a cohort of HFrEF patients from the ADHFD, we will randomize individual patients on the actionable list to usual VA care or a novel proactive panel management clinic. Clinicians will be trained on how to use the dashboard information to identify opportunities for optimization based on detailed chart review. The proactive panel management intervention will use clinicians to perform an electronic chart review and call patients impromptu at their discretion to evaluate HFrEF management and opportunities to optimize GDMT. Each panel management clinic is staffed by a single cardiovascular clinician or trainee with cardiology (PI) supervision. All patients will receive chart review or telehealth notes brought to the attention of primary care and cardiology clinicians. Patients randomized to the intervention will only receive one chart review during a half-day panel management clinic with follow-up of any laboratory results or diagnostic tests as required and referral to HF or general cardiology clinic as deemed appropriate. The control arm consists of the usual delivery of health services with routine scheduled appointments for primary care or cardiology.

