Study enrollment is based on the inclusion and exclusion criteria used to filter the ADHFD list. A list of actionable patients with HFrEF will be exported for randomization. The GDMT optimization score will be automated for each patient on the extracted list (**Table 1**). A sample of 300 patients will be selected with the lowest GDMT composite scores. Once the final sample of the study is determined, patients will be randomized to usual care or the intervention. Intervention patients will be divided into smaller lists of 10 to 15 patients. These smaller

lists will be assigned to proactive panel management clinics. Clinicians staffing the intervention clinics will review ADHFD data, review the electronic health record (EHR) and decide whether to proceed to evaluate and recommend treatment over the phone to patients directly. If clinicians did not have sufficient time to review all patients on their clinic list, they will be redistributed to future intervention clinics. Intervention clinics will be held until each patient assigned the intervention has a chart review or attempted telephone contact. A failure to contact a patient will trigger a letter to a patient or electronic communication to their primary care or cardiology clinician.

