Prior to each ADHFD telehealth clinic (half-day clinic lasting 4 to 4.5 hours), clinicians will be sent a secure email that will include a password-protected Excel document of 15 patients with exported clinical summary data from the ADHFD. Clinicians will be instructed to chart-review patients and decide if an opportunity exists to further optimize the receipt of GDMT. Clinicians will also be given a document providing guidance on the sequence of GDMT optimization based on latest guidelines and VA policies (Supplement S1 GDMT Guidance Document). If a patient does not qualify for further optimization (i.e. chart documentation of prior intolerance, patient preference), a short note in the electronic health record (EHR) will document the chart review and inform the primary care clinician that based on chart review, no opportunity currently exists but they may consider further GDMT titration in the future. If a patient appears to have an opportunity for further titration, the clinician is encouraged to call the patient to see if they are available to discuss their HF care. If the patient agrees, a telehealth visit will take place over phone or switch to video. A formal telehealth cardiology visit will occur at the time of care. If the patient is interested but does not have time for a visit, a brief telephone note will be placed and a request for a future cardiology clinic visit will be requested. If a formal telehealth visit occurs, clinicians will be asked to inquire about key details around medication titration (**Supplement S2 Interview Guide**). The data from chart review and interviews will be documented on a password-protected Excel document (**Supplement S3 Clinician Documentation Form**). Any medication addition or titration will have indicated laboratory labs ordered per usual care. Lastly, clinicians will also be asked to administer a short survey with each participant based on a template at the end of the call proactive phone call (**Supplement S2 Interview guide**). Primary care and regular cardiology clinicians will be notified of any changes in medication management in the EHR. The study's lead (BZ, AV) will be available by phone to answer questions or problems that arise during the clinic. Supervision of patient encounters by clinical pharmacists, medical trainees, or advanced practice nurse practitioners and study protocols will be BZ as the licensed and boarded general cardiologist.

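### Clinician time (secondary outcome 4) runs to the end of documentation, but form S3 defines its only end time as the end of the phone call, so the value can be too short for called patients and is undefined for patients not called

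*SAP*

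**What the plan says.** Item 4 of the secondary outcomes in SAP 4.2.2 is "Clinician time spent per patient from opening chart to end of patient-specific intervention and documentation". It serves an objective stated in Protocol section 3 and SAP 4.1, which is to assess clinician time per intervention against the usual clinic structure.

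The times are collected on form S3, which appears in Protocol section 9 and SAP section 15 with the same definitions:

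- Start Time: "Military time at onset of pre-chart".
- The end-time field, labelled Time (end call) in the definitions table: "Military time on completion of phone call". In the template row the same column is headed End Time.
- Phone Call Time: "Duration of successful phone or video visit".

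No field records when documentation is finished. SAP 5.4 lists the data taken from the dashboard, and clinician time is not among them. Neither document names another source for it.

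SAP 5.1 makes the call optional: clinicians review the chart and "call patients impromptu at their discretion to evaluate HFrEF management and opportunities to optimize GDMT". Where the review shows no room to optimize, "a short note in the electronic health record (EHR) will document the chart review and inform the primary care clinician", and no call is foreseen. Where a call is tried and fails, further work follows: "A failure to contact a patient will trigger a letter to a patient or electronic communication to their primary care or cardiology clinician".

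**The concern.** The outcome and the form that supplies it start the clock at the same point but stop it at different points. The outcome stops when the documentation is done; the form, as defined, stops when the call ends. Two consequences follow for anyone who applies the written definition. For a called patient, whatever is written or sent after hanging up is lost. For a patient who is reviewed but not called, the stopping event never occurs, so the duration cannot be computed.

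At stake is a named secondary outcome tied to a stated objective. Time per patient is one of the figures a health system would use to judge whether panel clinics are worth running. End times that were not recorded during a clinic may not be recoverable afterwards, so the wording matters before the clinics are held.

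**Working it through.** The plan gives no figure for clinician time, so there is nothing to reproduce. The check compares definitions, followed by simple arithmetic.

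**1. Start and stop points side by side**

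| | Outcome 4 (SAP 4.2.2) | Form S3, as defined |
|---|---|---|
| Start | Chart opened | Pre-charting begins |
| Stop | Intervention and documentation both finished | Phone call finished |

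The starts agree. The stops do not.

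**2. Called patients**

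Let *r* be the recorded time (end of call minus start) and *d* the minutes of patient-specific work done after the call. Time on the outcome's own definition is *r + d*, and the proportion missed is *d / (r + d)*. Since *d* cannot be negative, the recorded value is right (*d* = 0) or too short.

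The only times shown in the documents are in the template row: 13:55 to 14:15, so *r* = 20 minutes. The documents give no value for *d*; 0 to 8 minutes is an assumption.

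| *d* (assumed) | Time on outcome definition | Understatement |
|---|---|---|
| 0 min | 20 min | 0% |
| 3 min | 23 min | 3/23 = 13% |
| 8 min | 28 min | 8/28 = 29% |

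For scale, SAP 5.1 gives a half-day clinic of 4 to 4.5 hours and lists of 10 to 15 patients. That allows between 240/15 = 16 and 270/10 = 27 minutes per patient, so a few uncounted minutes would not be trivial.

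**3. Patients not called**

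The defined stopping event does not exist for them, so outcome 4 has no value under the written definition.

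**4. Effect on the mean**

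Suppose a share *p* of intervention patients is handled by chart review alone and drops out of the calculation. Let *C* and *R* be the true mean times for called and review-only patients, and let *d* now be the mean uncounted time among called patients.

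- Reported mean: *C − d*.
- True mean: *(1 − p)C + pR*.
- Reported minus true: *p(C − R) − d*.

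If review-only patients are quicker (*R < C*), the first term is positive and the second works against it. The reported mean is too high when *p(C − R)* exceeds *d* and too low when it does not. The documents give none of *p*, *C*, *R* or *d*, so the net direction cannot be determined.

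**The case against.** The case against making much of this has four parts.

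*Work after the call may be small.* The S2 interview guide places ordering medication, follow-up and laboratory tests before the closing questions and feedback, so as scripted the orders fall inside the call. The form is also meant to guide the review and the conversation, so some of the charting may be done during them. This stands: orders should not be counted as lost time, and *d* could be zero. It does not dispose of the point, because a letter or message triggered by failed contact necessarily follows the attempt, and nothing requires a visit note to be finished before the call ends.

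*The template suggests a broader reading.* Its column is headed End Time and comes after the list of actions performed. The sample row holds 1415 next to the comment "Straight to voicemail" and a mark for no response, so an end time can be entered without a completed conversation. This also stands: it is not established that values will be missing for patients who were not reached or not called. But the heading and the definition then disagree. Some clinicians may record the end of the work and others the end of the call, and pooling the two does not give the outcome as defined.

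*The 20-minute base is not trial data.* The sample row contradicts itself: it shows a 9-minute call and a feedback score alongside no response. The percentages are illustrations only.

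*The consequences are limited.* SAP section 9 specifies no analysis of clinician time. The one comparison with usual HF clinics, in SAP 9.3, concerns titrations per half-day and does not use this field.

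A reader might infer that time is certain to be understated, or that the error always favours the intervention. The documents support neither: *d* may be zero, and losing review-only patients can push the mean up as well as down. Nor do they show that a planned between-arm estimate is biased, since no measurement of time in usual clinics is specified.

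**Conclusion.** The mismatch is real and is present in both documents. Followed as defined, the form gives a called patient a time that is correct or too short, and gives a patient handled by review and note alone no time at all. The net bias in the mean has no known direction. The understatement for a called patient is 0% to 29% on a 20-minute illustrative row with an assumed 0 to 8 minutes of later work; both inputs are illustrative and neither is an estimate for this trial. The conclusion also assumes that form S3 is the source of the times. No other source is named, though none is ruled out.

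The primary analysis of the optimization score, the sample size, and the prescribing, hospitalization and mortality outcomes do not use this field. It should be corrected because an outcome definition and its data-collection form contradict each other and the correction is very cheap, but it does not threaten the trial's main conclusion.

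**What to change.** In S3, in both documents, make four changes:

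1. Use one label, End Time, in the template and in the definitions table, and define it as the time at which all patient-specific work is complete, including notes, letters and messages.
2. Require it for every intervention patient, whether a call was made, tried without success, or not made.
3. Keep Phone Call Time as the separate record of call duration.
4. State in SAP 4.2.2 that outcome 4 equals End Time minus pre-chart Start Time.

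The cost is a line or two of form wording and one sentence in the SAP, and no new data system is needed. The downside is that reported time per patient may become longer. If clinics have already run under the present wording, the report should say which end point was recorded and how many patients have no end time.
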